3. STUDY DESIGN

Activities to meet Aim 1. We will evaluate MMORE in a two-group randomized controlled design comparing treatment as usual (TAU) in partner maternity care practices with TAU + MMORE.

Participants will be 150 English-speaking consenting pregnant women aged 18 years and over who have a confirmed singleton pregnancy and are receiving perinatal services and medication for opioid use disorder at partner maternity care practices. We will aim to recruit women in their 2nd/early 3rd trimester of pregnancy.

After completion of the baseline assessment, consented participants will be randomly assigned to participate in the 8-session virtual yoga-mindfulness group intervention or to receive TAU only.

All intervention participants will be provided with a unique password-protected access link to the digital support materials, as well as detailed instructions for how to access the materials. A unique study code will allow us to monitor individual participant use of the support modules for analytic purposes.

All consented participants will complete assessments at baseline, post-intervention (8 weeks for TAU participants) and 3 months postpartum. Participants will complete assessments via a secured, de-identified and password-protected link accessed either on a study-provided laptop computer at a scheduled practice visit or via a protected email link to the user for completion at home or on another secure device with Internet access. Assessments will take approximately 20 minutes to complete. Based on formative data from phase 1 of this project, and other work the research team has conducted with the target population, we anticipate most women will have some access to the Internet either via a mobile phone, tablet, or home computer. If a participant cannot complete an assessment online, a paper version will be provided. The study staff will track ways that participants complete assessments. Participants will receive local gift cards for completion of each assessment.

Activities to meet Aim 2. All study participants (TAU and TAU+MMORE) will complete brief mobile assessments at the end of each week of their assigned cohort period. Assessments will be completed using either a mobile device or computer. Participants will receive a prompt (near end of the week) to complete the assessment. The encrypted, password-protected weekly brief assessment will include items to assess the following:

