5. STUDY INTERVENTIONS

5.1 Interventions, Administration, and Duration

Mindful Moms: Yoga Mindfulness Intervention. The significant restrictions to in-person delivery of services at practice partner settings and continued institutional barriers to in-person research at partner settings due to the ongoing Covid pandemic have necessitated the need for alternative safe intervention delivery strategies for the Mindful Moms intervention. After consultation with our partner practice stakeholders and women with lived experience from our study advisory committee, we are modifying the intervention delivery mode to include virtual delivery of the intervention. We will deliver the group intervention virtually through a secured

Dartmouth-based video conferencing software (Zoom). The virtual intervention protocol will be 8 sessions, approximately 60-minutes in duration, conducted over the course of 10 weeks. Lead Instructor [name], professionally trained and certified in prenatal and trauma-informed yoga, will implement the group protocol sessions at the designated location. Sessions will be attended by at least one study team member. Sessions will be video or audio recorded (participants de-identified) to allow for assessment of fidelity in delivery of protocol.

All intervention participants will be provided with a tablet and mobile hotspot if needed in order to be able to access the virtual intervention sessions. All intervention participants will complete a training with research study staff about how to use the videoconferencing software. All intervention participants will be provided with a unique password-protected access link to the online support materials, as well as detailed instructions for how to access the materials. A unique study code will allow us to monitor individual participant use of the support modules for analytic purposes.

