6. STUDY PROCEDURES

6.1 Schedule of Evaluations

Assessment	BL	Intervention	Post	3M PP	Final Evaluation
Eligibility: Consent/Enrollment	X				
Demographics	X				
Current physical conditions that could be considered	x				
AE					
Opioid Abstinence	X		X	X	
MOUD Treatment Retention	X		X	X	
Depression	X		X	X	
Anxiety	X		X	X	
Stress	X		X	X	
Mindfulness	X		X	X	
Pain Perception	X		X	X	
Quality of life	X		X	X	
Substance use (past 3 months, past 30 days)	X		X	X	
Weekly Assessments (craving, mood, stress, mindfulness)		X			
Adverse Events		X	X	X	
Experiences of Care (qualitative)				X	
Fidelity, Acceptability, Reach, Feasibility, Sustainability (Practice Level)					X
Organization Readiness for Implementing Change (Practice Level)		X			X
Program Sustainability (Practice Level)					X

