Treatment Retention. Self-reported adherence to medication for opioid use disorder will be assessed by an adaptation of items from the well-established Adherence to Medication questionnaire originally developed for assessing adherence to antiviral medications among persons with HIV/AIDS. (i.e., when was the last time you skipped buprenorphine medication? [past 2 days, within the past 2 weeks, 2-4 weeks ago, 1-3 months ago, never skipped past 3 months]. Participants will also report how often they attended group/individual counseling in the past 3 months [every week, every other week, once a month, less than once a month].

Opioid abstinence. The reliability of self-report of substance use for pregnant and parenting women is especially complicated due to well-founded fears of child protective service involvement and potential loss of children. That said, when research studies are well-conducted and assurances for protection of participant privacy are clear and conveyed with messaging informed by community partners with lived experience, women do reliably self-report their use behaviors.

Opioid use will be assessed with relevant items from the Alcohol, Smoking and Substance Involvement Screening Test, aligned with relevant timeframes (baseline: past 6 months, post-intervention and 3 month postpartum: past 3 months). Opioid use disorder severity will be assessed with items corresponding to DSM-V diagnostic criteria.

Secondary End Points:

Other substance use:

Self-reported frequency and quantity of opioid and other substance use (including alcohol, marijuana, and tobacco) will be assessed with the Alcohol, Smoking and Substance Involvement Screening Test, aligned with relevant timeframes (baseline: past 6 months, post-intervention, 3 month postpartum: since last survey).

Mental Health:

Depression will be assessed using the Edinburgh Prenatal and Postnatal Depression Scales, both of which have been used extensively with the target population.

Anxiety will be assessed with the Generalized Anxiety Disorder Scale (GAD-7)², a psychometrically sound instrument routinely used in general health care settings.

Stress will be assessed with the Perceived Stress Scale,³ a psychometrically sound instrument that has been used in other studies of contemplative interventions with pregnant women⁴⁻⁷.

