9.5.2 Secondary Outcomes

Other substance use.

Self-reported frequency and quantity of opioid and other substance use (including alcohol, marijuana, and tobacco) will be assessed with the Alcohol, Smoking and Substance Involvement Screening Test (ASSIST), aligned with relevant timeframes (baseline: past 6 months, post-intervention and 3 month postpartum: past 3 months).

Mental Health:

Depression will be assessed using the Edinburgh Prenatal and Postnatal Depression Scales, both of which have been used extensively with the target population.

Anxiety will be assessed with the Generalized Anxiety Disorder Scale (GAD-7)², a psychometrically sound instrument routinely used in general health care settings.

Stress will be assessed with the Perceived Stress Scale,³ a psychometrically sound instrument that has been used in other studies of contemplative interventions with pregnant women⁴⁻⁷.

Posttraumatic stress will be assessed with the abbreviated PTSD Checklist (PCL-5), a screening instrument developed for primary care and other general medical settings.⁸

Mindfulness. Mindfulness will be assessed with the Mindful Attention Awareness Scale.¹³ This instrument has been used with demonstrated strong psychometrics in mindfulness intervention studies with pregnant women⁴ and substance using populations⁹⁻¹². *Acceptance* will be measured with the Acceptance and Action Questionnaire (AAQ), which has been used in other mindfulness studies with substance-using populations^{9,12}.

Quality of Life. Quality of life will be assessed with the World Health Organization QoL BRF, a widely used instrument with demonstrated validity and reliability with pregnant and early postpartum women.

Pain Perception. Pain Perception will be assessed by a widely used visual analog scale (VAS) used in other studies with pregnant women. Participants report point areas and levels of pain on a scale from 0 (no pain) to 10 (worst possible pain) and anchored with descriptive faces.

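### At post-intervention the self-report opioid item looks back 3 months over an interval of nominally 8 to 10 weeks, so it can count use before randomisation, and other sections give different windows

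*Combined protocol and SAP*

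**What the plan says.** Section 6.2, under the self-report primary end points, measures opioid use with ASSIST items over these periods: "baseline: past 6 months, post-intervention and 3 month postpartum: past 3 months". Further down, the self-report secondary end point covers "Self-reported frequency and quantity of opioid and other substance use (including alcohol, marijuana, and tobacco". It uses the same instrument but gives "baseline: past 6 months, post-intervention, 3 month postpartum: since last survey". Section 9.5.2 restates that secondary end point with "post-intervention and 3 month postpartum: past 3 months". The schedule in section 6.1 has one row, "Substance use (past 3 months, past 30 days", ticked at baseline, post-intervention and 3 months postpartum.

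On timing, section 3 places the surveys at baseline, "post-intervention (8 weeks for TAU participants) and 3 months postpartum". Section 5.1 says the eight MMORE sessions are "conducted over the course of 10 weeks". Section 9.6 calls the first follow-up the 8-week time point for both arms. Section 6.2.2 puts randomisation after baseline and starts a group once 8-10 women have enrolled, with a new group at least every 8 weeks.

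On the outcome, section 9.5.1 defines abstinence as weeks of consistent abstinence during the study and continuity between successive assessments. Section 10.1 takes it from both the chart and self-report.

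**The concern.** A follow-up question should cover time after randomisation. Here the look-back is longer than the nominal interval it follows, so a woman who used opioids shortly before enrolling and not since can truthfully report use at post-intervention. That use cannot be an effect of treatment. Once the 3-month question has been answered, the earlier weeks cannot be separated out.

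Two different harms are possible, and they belong to different schedules. If both arms are surveyed at the same time, both pick up the same earlier weeks and a true difference shrinks. If TAU is surveyed sooner than MMORE from the same origin, TAU picks up more earlier weeks and the comparison tilts towards MMORE.

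The conflicting windows are a separate problem. One questionnaire cannot meet sections 6.1, 6.2 and 9.5.2 together, and a fixed 3-month window does not match the continuity definition in section 9.5.1.

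**Working it through.** **Plan's own figure.** Section 9.2 states 80% power for 80% v 94% abstinent over three time points with within-person correlation 0.5. Recruiting 150 with 20% attrition leaves 120, or 60 per arm. The design effect is (1 + 2 × 0.5)/3 = 0.667, so the effective size is 60/0.667 = 90 per arm. A two-sided 0.05 test of two proportions then has power 0.803, so the figure reproduces. (Two-sided 0.05 is stated for weeks abstinent and assumed here.) At one time point with 60 per arm, power is 0.63. That is the reference for the post-intervention contrast alone.

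**Overlap.** Weeks before baseline = window − weeks from baseline to survey.
- 3 months as 13 weeks: 13 − 8 = 5 weeks (5/13 = 38%); 13 − 10 = 3 weeks (3/13 = 23%).
- 3 months as 12 weeks: 12 − 8 = 4 weeks (33%); 12 − 10 = 2 weeks (17%).

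**Waiting time, if the survey clock starts with the group.** The section 6.2.2 rate of 12 per month is about 2.76 per week. Enrolling 8-10 women takes 8/2.76 = 2.9 to 10/2.76 = 3.6 weeks. The first to enrol in such a group is surveyed at up to 8 + 3.6 = 11.6 weeks (1.4 weeks of overlap left) or 10 + 3.6 = 13.6 weeks (none). A wait of 5 weeks (8-week timing) or 3 weeks (10-week timing) removes the overlap. If waits were instead uniform over 0-8 weeks, about 5/8 = 63% or 3/8 = 38% of women would still have some.

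**Case A: same survey time in both arms.** Assume a share q of otherwise abstinent women, equal in both arms, report use only from the pre-baseline part. The contrast is 80(1 − q) v 94(1 − q), at one time point with 60 per arm:
- q = 2%: 78.4 v 92.1, power 0.57
- q = 5%: 76.0 v 89.3, power 0.49
- q = 10%: 72.0 v 84.6, power 0.39

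**Case B: TAU at 8 weeks, MMORE at 10, same origin, no true effect.** Assume 80% are abstinent since baseline in both arms, and a weekly probability h of pre-baseline use among them. The false difference is 0.80 × [(1 − h)^3 − (1 − h)^5]:
- h = 1%: 1.5 points
- h = 2%: 3.0 points
- h = 5%: 6.7 points, each in favour of MMORE

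**Case B with a true effect.** Suppose pre-baseline use runs at the TAU rate. TAU becomes 0.80 × 0.80^(5/8) = 69.6%. MMORE becomes 0.94 × 0.80^(3/8) = 86.5% at the same weekly rate, or 0.94 × 0.80^(3/10) = 87.9% if that rate is spread over 10 weeks. The gap widens from 14 points to 16.9 or 18.3, with power about 0.61 or 0.69. Unequal timing therefore biases the contrast rather than diluting it.

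The values of q and h, and the use of the TAU rate before baseline, are assumptions. The documents give no pre-baseline rates.

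**The case against.** The strongest reply is that the affected measure may not drive the primary analysis. Section 6.2 also measures abstinence by weekly urine toxicology from the chart, which has no recall window and supplies the weekly count in section 9.5.1 directly. No rule turns the ASSIST items into abstinent or not abstinent. This stands as a limit on the consequence. It does not remove the point, because section 6.2 lists self-report under primary end points and neither section 9.6 nor section 10.1 says which source enters the GEE.

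The arm difference is also only one reading. Section 9.6 uses a single 8-week time point, and section 3 does not say when TAU's 8 weeks begin. This stands, so bias towards MMORE is conditional.

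The conflict between windows can be overcounted. Six months applies only at baseline, and the schedule row does not name ASSIST and is separate from the opioid abstinence row. The clear clash is between 3 months and "post-intervention, 3 month postpartum: since last survey" for the same instrument, in items that both cover opioids.

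A reader might go further and infer a large power loss. Applying the TAU rate to the earlier weeks in both arms gives 69.6 v 81.8% (power 34%) at 8 weeks, or 74.8 v 87.9% (45%) at 10. The documents do not support that as an expected result. It needs both arms surveyed at the same time, so it cannot be combined with the arm-bias argument. It also treats earlier and later use in the same woman as independent, whereas section 9.2 assumes a correlation of 0.5. Nor do the documents support a pre-baseline rate two or three times the later one, which would be needed to argue for a larger bias.

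**Conclusion.** The point holds in a limited form. On the nominal schedule the 3-month window reaches up to about 5 weeks (8-week survey) or 3 weeks (10-week survey) before randomisation for women who start soon after baseline. It reaches less far, or not at all, for those who wait. Pre-randomisation use can therefore be counted as an outcome in a self-report item listed as primary. The result is mainly dilution if survey times are equal, or a possible tilt towards MMORE if they are 8 and 10 weeks from one origin. These are alternatives, and the figures above only illustrate them. It would be wrong to conclude that the primary analysis is biased or underpowered by a known amount, because toxicology is unaffected and the source of the binary outcome is unstated. The disagreement among sections 6.1, 6.2 and 9.5.2, and the mismatch with section 9.5.1, rest on the text alone and need no assumption.

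**What to change.** - In sections 6.1, 6.2 and 9.5.2, at post-intervention, ask about use since the previous survey (that is, since baseline) for the opioid and other-substance items in both arms. Section 6.2 already contains this window. It brings the overlap to zero and fits section 9.5.1.
- Give one window for the 3-month postpartum survey, worded identically in the three sections.
- Time the TAU post-intervention survey to the end of the course of the MMORE group in the same cohort, so that windows are equal by arm. Section 3 already refers to an assigned cohort period for both arms. A fixed number of weeks after randomisation would be a poorer anchor: group starts vary, so some MMORE women could be surveyed before their course ends.
- Record survey dates.
- State in section 9.6 whether urine toxicology or self-report defines binary abstinence.

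The cost is a protocol edit, new survey wording and scheduling TAU surveys by cohort. The sample size does not change. The drawback is that window length varies slightly between women, which the survey dates will show.

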6.2.1 Screening Evaluation

Consenting Procedure

Interested participants will contact one of the project coordinatorss via email or phone to review the study procedures.

The project coordinator will review all aspects of the ICF with the candidate, checking for comprehension throughout, and will answer the candidate's questions. Additionally, the project coordinator will offer the candidate the opportunity to personally read the ICF over in more detail and will provide the candidate sufficient time to review and ultimately decide if she is willing to participate.

Assessing Comprehension

After allowing the candidate to review the ICF, and answering any preliminary questions, the project coordinator may ask the candidate the following questions to assess comprehension:

- Please describe in your own words the purpose of this study.
- Just so that I'm sure you understand, please explain to me what you think we're asking you to do.
- What is the possible benefit to you of participating in this study? What are the possible risks?
- What more would you like to know?

If the candidate answers all questions correctly, the project coordinator will answer any additional questions and the participant will indicate consent by marking the check box on the consent form. A waiver of signed consent was requested and approved by the Dartmouth IRB. The project coordinator will sign the consent form to indicate witness of consent and will provide the participant with a duplicate of the consent form.

If the candidate answers any questions incorrectly, the project coordinator will review the correct responses with candidate until comprehension is ensured and then proceed with obtaining consent.

If, after assistance and review of correct responses, the candidate is unable to demonstrate a basic understanding of the study, the candidate will be deemed ineligible to participate in the study. The project coordinator will thank the candidate and provide her with a list of local resources.

After informed consent has been obtained, the project coordinator will assign the participant a study ID. This study ID will be used for the entirety of the study to identify the participant. The master list that stores the study ID and participant information will be stored in the lead project coordinator's password protected computer in a password protected file.

Participants will complete the baseline assessment upon consent.

6.2.2 Enrollment, Baseline, and/or Randomization

Enrollment

In this study, the enrollment date will be the date that all of the screening criteria were met, and the individual consents to participate.

Baseline Assessments

Participants will complete the baseline assessment upon consenting to participate in the study. The project coordinators will administer the baseline assessment to the participant through a secure online survey. For participants who do not wish to complete the survey online, the project coordinator will arrange for either a phone interview with the participant to complete the survey or will mail the participant the survey along with a self-addressed and stamped envelope for the participant to return the survey. Both forms of the assessment will be coded with a unique study ID.

Randomization

Following baseline completion, participants will be randomized to condition by the lead project coordinator. The lead project coordinator will meet via phone with participants assigned to the MMORE condition to explain the condition. Participants in the MMORE condition will receive a secure password-protected access to the digital companion features.

Randomization will be conducted via permuted blocks. Once 8-10 participants have enrolled, an intervention will commence for that cohort. The randomization block size would be random, with blocks of size 4, 6, and 8. In thinking about how best to implement our group randomization plan in the context of the reality of recruitment of this high-risk target population, we have developed a plan of ongoing recruitment and starting a new group at least every 8 weeks. With a conservative recruitment

rate of 12 participants per month, we do not anticipate a good deal of differential lag-time between recruitment into the study, completion of baseline, randomization, and start of a new group.

6.2.3 Blinding

The study will be blind to the Principal Investigator, the statistician, and to those on the team responsible for participant data collection. We will work to try to blind clinicians delivering TAU to participant assignment but there is a chance that patients will reveal their condition to clinicians despite our best efforts. To achieve blindness, treatment assignment will be done by the lead project coordinator, who will not be directly involved in evaluation or data collection. Survey data collection will be conducted by the project coordinator who will be blinded to participant treatment assignment. Participant self-report surveys will be implemented using secured online survey software, which will significantly limit the potential of the project coordinator to introduce bias.

Stakeholder	Blind Status	Involved in Data Collection?	Steps to ensure blindness
TAU Clinicians	Potentially un-blinded	No	Patient participants may indicate to their clinician that participating in study. Clinicians will be instructed not to specifically ask patients about study.
PI	Blinded	No	The PI will not be involved in the group assignment or collection of data; analyses will be conducted when data are unlocked.
Statistician	Blinded	No • Will conduct analyses	Will not have access to randomization algorithm key
Project Coordinator	Blinded, with possibility of being inadvertently un-blinded	Yes	
 Will be instructed not to inquire with participants about study. Will report instances of learning status Assessments conducted via secured online survey software.
Lead project coordinator	Un-blinded • Knows random assignment • Introduces participants to their treatment condition	No	

	
 • Prepares necessary reports 		
--	--	--	--

